## 7.2. Secondary Efficacy Analyses

### 7.2.1. Endpoint / Variables

Secondary Efficacy Endpoints are the following items in Blind Phase:

- MAS scores in the elbow, finger, thumb and wrist flexors.
- Change from baseline in MAS scores
- Responder rate of MAS in the elbow, finger, thumb and wrist flexors.
- DAS score (Main Assessment Parameter)
- Change from baseline in DAS score (Main Assessment Parameter)

### 7.2.2. Summary Measure

Summary Measures are as below.

- The differences in the responder rate of MAS scores
- The differences in the least square means of changes from baseline in MAS scores
- The differences in the least square means of changes from baseline in DAS scores

### 7.2.3. Population of Interest

The secondary efficacy analyses will be based on the Intent-To-Treat 1 population, unless otherwise specified.

The secondary efficacy analyses will be performed for only double blind phase. All efficacy analyses for open -label phase and other endpoints for double blind phase will be done as exploratory.

## CONFIDENTIAL

207660

Unless specified otherwise, the data up to Week 12 of treatment will be summarized during the double-blind period. This is because this study allows to re-treat. In other words, after 12 weeks, only participants who have a smaller MAS score would remain and the difference of the change from baseline in MAS between 240 units and 400 units would be attenuated. Therefore, the data up to Week 12 of initial treatment will be analysed as secondary statistical analyses. This is the case for exploratory analyses for open label period (i.e. the data up to week 12 of re-treatment will be summarized). Listing will include the data after week 12 of treatment/re-treatment.

#### 7.2.4. Strategy for Intercurrent (Post-Randomization) Events

Intercurrent event: early withdrawal from study.

Strategy for dichotomous data: the participant will be regarded as a non-responder.

Strategy for continuous data: the missing data will be removed from the analyses.

#### 7.2.5. Statistical Analyses / Methods

Details of the planned displays are provided in [Appendix 12: List of Data Displays](#) and will be based on GSK data standards and statistical principles.

Unless otherwise specified, endpoints / variables defined in Section [7.2.1](#) will be summarised using descriptive statistics, graphically presented and listed.

##### 7.2.5.1. Statistical Methodology Specification

Secondary Efficacy Analysis
Endpoint / Variables

 
Change from baseline in MAS in each joint and DAS (Main Assessment Parameter) scores
 

Model Specification

 
The endpoint will be analyzed using a mixed model for repeated measures (MMRM)
 
Terms fitted in the MMRM will include the items below as fixed effects. 
 
Categorical effect 
 
Treatment
 
Visit
 
Treatment-by-visit interaction
 
 
 
Continuous effect 
 
Baseline value in MAS of each joint or in DAS (Main Assessment Parameter)
 
Baseline-by-visit interaction
 
 
 
 
 
An unstructured variance structure will be used to model the within-participant errors, shared across treatments.
 
The empirical sandwich estimator will be used to estimate the standard errors.
 

Model Checking & Diagnostics

 
If the model will not converge with unstructured variance, AR(1) variance structure can be
 

CONFIDENTIAL

207660

Secondary Efficacy Analysis
used.
Model Results Presentation

 
Adjusted means (least square means) and corresponding standard errors of means will be presented for each treatment by visit, together with estimated treatment differences (400 units – 240 units) and the corresponding 95% CI.
 

Data included in Model

 
The dataset including only data until week 12 after the first treatment will be used.
 

Secondary Efficacy Analysis
Endpoint / Variables

 
Responder Rate of MAS score in each joint at all visit
 
Responder is defined as well as primary endpoint.
 
For the elbow, finger and wrist flexors. 
 
Responder rate (%) = (Number of Responders) / (Number of participants in ITT1 population) x 100
 
 
 
For the thumb flexors 
 
Responder rate (%) = (Number of Responders) / (Number of Participants in ITT1 population, except for the participants of which thumb was not evaluable, x 100.
 
In case that the thumb was not evaluable, MAS score data will be entered as “Not Applicable”.
 
 
 

Model Specification

 
See primary endpoint section.
 

Data Convention

 
See primary endpoint section.
 

Supportive Statistical Analyses

 
See supportive statistical analyses for primary efficacy analyses section.
 
Baseline MAS score of the elbow as a stratification factor will be used for the Mantel Haenszel Estimator, regardless of the Responder rate of MAS score in the other joint.
 

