## CONFIDENTIAL

207660

Overview of Study Design and Key Features	
	
muscles that act on the finger (including thumb flexors) and wrist flexors, and 160 units into the muscles that act on the elbow flexors. A total of 400 units of the product will be injected.
 
 
• In the 240-unit group, 240 units of the product will be injected into the muscles that act on the finger (including thumb flexors) and wrist flexors. Placebo will be injected into the muscles that act on the elbow flexors. A total of 240 units of the product will be injected.
 
• In the Open-label phase, a total of 400 units will be injected in both groups. 
 
• The product can be injected up to 3 times after completion of Part 1 in the blind phase. Participants whom the investigator considers as eligible for the injections will be treated. The next injections cannot be performed until the eligibility of the participant has been confirmed by the investigator.
 
• The muscle to be injected and the dose will be decided by the investigator based on the patient's symptoms, and a total dose of 400 units of the product will be injected in a divided dose. For the muscles that the investigator considers as unnecessary to be treated, an injection may be skipped. The involving muscle and the dose do not have to be same each time always.
 
 
 

Treatment Assignment	
 
• Number of participants (randomized participants): 120 (60 per group)
 
• GSK RandAll NG will be used to generate the randomization schedule.
 
• The randomization will be stratified by the MAS score (3 or 4) in the elbow flexors at Day1
 

Interim Analysis	
 
• Interim analysis is planned in this study as described in 3.1.
 

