**7.1.5.1. Statistical Methodology Specification**

Endpoint / Variables

 
• Responder Rate of MAS in the elbow flexors at Week 6 of the initial dose
 

Model Specification

 
• To summarize the primary endpoint without statistical model 
 
○ The primary endpoint will be calculated as the proportion of participants whose MAS score decreased by at least 1 level from the baseline in the ITT1 population.
 
○ The intergroup difference in the responder rate and its 95% confidence interval (Wald-type) will be computed.
 
 
 

Data Convention

 
• The MAS scores, 0, 1, 1+, 2, 3 and 4 will be encoded to 0, 1, 2, 3, 4 and 5, respectively, for the analyses.
 

Definition of Responder and Responder rate

“Responder” is defined as a participant whose MAS score decrease by at least 1 level from the baseline.
 
Responder Rate will be calculated as below.
 
Responder Rate (%) = (Number of Responders) / (Number of participants in ITT1 population) x 100
 
 
• If MAS score of a given participant is missing at Week 6, then this participant will be regarded as a non-responder.
 

Model Results Presentation

 
• The difference in the responder rate (400 units – 240 units) and its associated 95% CI will be presented.
 

Subgroup Analyses (Rehabilitation)

 
Subgroup analyses will be performed by baseline rehabilitation in the Section 5.4.
 
The difference (400 units – 240 units) and its 95% CI will be presented.
 

Subgroup Analyses (baseline MAS score)

 
Subgroup analyses will be performed by baseline MAS score of the elbow (3 or 4) used as randomization strata.
 
The difference (400 units – 240 units) and its 95% CI will be presented.
 

Supportive Analyses

 
The difference in the responder rate will be estimated using Mantel-Haenszel method to consider a stratification factor, that is baseline MAS score of the elbow (3 or 4).
 
Mantel-Haenszel rate difference (400 units – 240 units) and its 95% CI will be calculated.
 

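### Finger, wrist and thumb responder differences are never adjusted for that joint's own baseline MAS, so the supportive estimate may be less precise than it could be

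*SAP*

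**What the plan says.** All references are to the amended SAP.

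- **Main responder analysis.** Section 7.1.5.1 states: "The intergroup difference in the responder rate and its 95% confidence interval (Wald-type) will be computed". Section 7.2.5.1 sends the secondary responder rates back to that specification, so the main interval for finger, wrist and thumb is unstratified.
- **Supportive responder analysis.** Section 7.1.5.1 estimates the difference "using Mantel-Haenszel method to consider a stratification factor, that is baseline MAS score of the elbow (3 or 4"). Section 7.2.5.1 carries this over ("See supportive statistical analyses for primary efficacy analyses section") and adds: "Baseline MAS score of the elbow as a stratification factor will be used for the Mantel Haenszel Estimator, regardless of the Responder rate" in the other joint.
- **Design.** Section 2.3: "The randomization will be stratified by the MAS score (3 or 4) in the elbow flexors at Day1", and "Number of participants (randomized participants): 120 (60 per group"). Both groups receive the same 240 units in the finger, thumb and wrist muscles.
- **Responder.** A participant "whose MAS score decrease by at least 1 level from the baseline", on MAS grades 0, 1, 1+, 2, 3, 4 coded 0 to 5. For finger and wrist the denominator is all of ITT1. For thumb, participants whose thumb could not be evaluated are left out.
- **Own-joint baseline elsewhere.** The MMRM of change in MAS in section 7.2.5.1 has as a continuous covariate "Baseline value in MAS of each joint or in DAS (Main Assessment Parameter"), plus its interaction with visit. Section 6.4 and Table 1.09 summarise baseline MAS for finger, thumb, wrist and elbow by group.

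**The concern.** Two analyses of the same joint, built from the same scores, adjust for different baselines. The change-score model uses the joint's own starting level. The responder analysis uses the elbow's level or nothing. How likely a wrist or finger is to drop a level may well depend on where it starts. At a starting score of 0 it cannot drop, yet such a participant stays in the finger and wrist denominators as a certain non-responder. Randomisation balances the elbow score only.

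Because both arms receive the same dose in these joints, the expected difference may be small. A chance imbalance in own-joint baseline could then be large relative to it. What is at stake is the precision and readability of a supportive, descriptive estimate, not a test result.

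**Working it through.** The SAP gives no response rates, interval widths or power for these endpoints, so there is no planned figure to reproduce. It also gives no baseline distribution or entry requirement for finger, wrist or thumb. The only inputs from the SAP are 60 per arm, 1:1 allocation, the elbow stratum and the responder rule. All rates and baseline distributions below are assumptions.

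**1. Large-sample effect on width.** With response probability p(b) at own baseline b and mean p̄, the ratio of adjusted to unadjusted width is √(1 − R²), where R² = Var[p(b)] / [p̄(1 − p̄)].

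- *Steep case:* baseline ≤1, 2, 3, 4 in 10/40/35/15%, response 10/50/70/75%. p̄ = 0.5675, Var = 0.0348, p̄(1 − p̄) = 0.2454, R² = 0.142, ratio 0.926. About 7% narrower.
- *Flatter case, no scores ≤1:* baseline 2, 3, 4 in 45/40/15%, response 50/65/75%. R² = 0.037, ratio 0.981. About 2% narrower.
- *Steep case with own baseline pooled as ≤2, 3, 4:* weights 0.50/0.35/0.15, response 0.42/0.70/0.75. R² = 0.090, ratio 0.954. About 4.6% narrower, because pooling merges the group that produces most of the gain.

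**2. Simulation.** 4,000 trials per scenario, 60 per arm, blocks of 4 within elbow stratum, 30% with elbow MAS 4, a modest elbow-joint correlation, no treatment effect, Sato variance for Mantel-Haenszel. Mean 95% half-width in percentage points:

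| Assumed own-joint baseline and response | By elbow | By own joint | Change |
|---|---|---|---|
| No zeros, 70% at every level | 16.25 | 16.45 | +1.2% |
| No zeros, 60–75% | 16.61 | 16.76 | +0.9% |
| No zeros, 50–80% | 16.91 | 16.87 | −0.2% |
| Two equal levels, 40% and 80% | 17.34 | 15.88 | −8.4% |
| 5% at baseline 0, others 70% | 16.75 | 15.96 | −4.7% |
| 10% at baseline 0, others 70% | 17.11 | 15.54 | −9.2% |
| 20% at baseline 0, others 70% | 17.57 | 14.67 | −16.5% |

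The elbow-stratified interval was within 0.04 points of the unadjusted Wald interval in every scenario. Under these assumptions the elbow stratum adds almost no precision for the other joints.

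Crossing elbow stratum with own baseline in Mantel-Haenszel did slightly worse than own baseline alone. It ran from 16.25 to 16.66 (+2.5%) with no gradient, to 17.57 to 14.79 (−15.8%) with 20% zeros.

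**3. Chance imbalance.** For a low-baseline group of 10%, the SD of the between-arm difference in its share is √(2 × 0.10 × 0.90 / 60) = 0.0548, or 5.5 points (about three participants in 60). In the steep case the others respond at (0.5675 − 0.01)/0.90 = 61.9%, a gap of 51.9 points from 10%. The shift is 0.0548 × 51.9 = 2.8 points.

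The unadjusted half-width in the same case is 1.96 × √(2 × 0.2454 / 60) = 17.7 points, so the shift is about 16% of it.

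**The case against.** The strongest reply is that the SAP's choice is sound. The elbow score is the randomisation stratum, and section 7.1.5.1 says the Mantel-Haenszel estimate is there to reflect that factor. Applying it to every joint is explicit and pre-specified. The analysis is supportive, and section 5.5 confirms that no hypothesis is tested. Under randomisation, leaving out a prognostic baseline does not bias the risk difference, and the 95% interval already allows for chance imbalance. Table 1.09 would show an imbalance, and the MMRM covers own-joint baseline for the change score. All of this stands, and it keeps the point minor.

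Three stronger readings are tempting, and the SAP does not support them.

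- A reader might infer that own baseline generally limits whether a joint can respond. On the coded scale only a score of 0 rules response out, and the SAP does not show whether such participants are enrolled.
- A reader might infer that the intervals are certainly wider than needed. With no zeros and a flat or weak gradient, adjustment makes them slightly wider.
- A reader might see the MMRM and the responder analysis as contradicting each other. They address different endpoints, and different covariates are not an inconsistency.

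The reply does not remove the fact that neither responder estimate for these joints, main or supportive, uses a collected baseline that the plan itself treats as worth adjusting for. A supportive estimate almost identical to the crude one says little about robustness.

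**Conclusion.** The point holds as a minor matter of efficiency and robustness for the finger, wrist and thumb responder differences. There is no error or bias, and the primary elbow analysis is untouched: for the elbow, the stratum is the joint's own baseline.

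The possible change in interval width runs from about 1% wider to about 17% narrower when own-joint baseline replaces the elbow stratum. Where a trial falls in that range depends on two facts not in the SAP: the share of participants at baseline 0, and how steeply response depends on baseline. The 2.8-point shift depends on the assumed 10% low-baseline group and its assumed 10% response. The regression-standardised estimate proposed below was not itself simulated. The figures show what own-joint baseline can contribute, not that estimator's exact performance.

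**What to change.** In section 7.2.5.1, under the supportive responder analyses, keep the elbow-stratified Mantel-Haenszel estimate. For finger, wrist and thumb, add a pre-specified risk difference (400 units minus 240 units) with 95% CI, standardised from a logistic model with treatment, elbow stratum (3 or 4) and that joint's own baseline MAS on the 0–5 coding. State how baseline enters (score or categories) and the rule for collapsing sparse levels. Do not pool the lowest scores with MAS 2 unless counts require it. Retain the existing denominators and non-responder rule, and keep the elbow stratum alone for the elbow.

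A model is preferable to crossed Mantel-Haenszel strata: even three own-baseline groups by two elbow strata make six cells in 120 participants. Naming the covariate now also avoids choosing it after an imbalance has been seen, which section 5.4.1 leaves open by allowing additional covariates to be considered.

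The cost is a few lines of text and one extra supportive estimate per joint and visit from data already collected. Some levels may need collapsing, and a category with no responders would make a categorical model unstable. If own baseline is only weakly prognostic, there may be little or no gain in precision.

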### 7.3. Exploratory Efficacy Analyses

#### 7.3.1. Modified Ashworth Scale (MAS)

These analyses will be based on ITT 2, 3 and 4 populations.

Values and changes from baseline in MAS scores in finger, thumb, wrist and elbow will be summarised using descriptive statistics, graphically presented and listed by visit and treatment cycle. In addition, the number and percentage of Responder in MAS score of each joint will be presented by visit and treatment cycle including graphically. The

**CONFIDENTIAL**

207660

Responder rate will be the proportion of the responder in the corresponding population, except for the participant of which joint was not evaluable. MAS score values in pronation of the forearm and shoulder flexors will be summarised using descriptive statistics, graphically presented and listed by visit and treatment cycle. Data up to Week 12 in each treatment cycle will be used for summary tables and Figures, whereas all data will be listed.

**7.3.2. Numeric Rating Scale (NRS) for pain**

These analyses will be based on ITT 1, 2, 3 and 4 populations.

Values and changes from baseline in NRS of the elbow for pain will be summarised using descriptive statistics, graphically presented and listed by visit, treatment cycle and evaluated part. NRS values except for that of elbow flexors will be summarised using descriptive statistics, graphically presented and listed by visit and treatment cycle. Data up to Week 12 in each treatment cycle will be used for summary tables and Figures, whereas all data will be listed.

**7.3.3. Disability Assessment Scale (DAS)**

These analyses will be based on ITT 1, 2, 3 and 4 populations.

Values and changes from baseline in all items of DAS will be summarised using descriptive statistics, graphically presented and listed by visit and treatment cycle. Data up to Week 12 in each treatment cycle will be used for summary tables and Figures, whereas all data will be listed.

**7.3.4. Clinical Global Impression of Change (CGI) of functional disability**

These analyses will be based on ITT 1, 2, 3 and 4 populations.

Values of the variables below will be summarised using descriptive statistics, graphically presented and listed by visit and treatment cycle. Data up to Week 12 in each treatment cycle will be used for summary tables and Figures, whereas all data will be listed.

CGI of functional disability by an investigator

CGI of functional disability by a patient

**7.3.5. Patient-Reported Benefit of Injection**

These analyses will be based on ITT 1, 2, 3 and 4 populations.

The number and percentage of patient-reported benefit of injection will be presented and listed by visit and treatment cycle.

CONFIDENTIAL

207660

### **7.3.6. Time to Patient-Reported Onset of Spasticity Symptom Relief**

These analyses will be based on ITT 1, 2, 3 and 4 populations.

Time to event data will be summarized using the descriptive statistics below and listed.

- The number of events and censored cases.
- Median survival time with the associated 95% CI.
- 25% and 75% survival time.

Survival analyses will be conducted using a Kaplan-Meier method. To graphically compare the survival functions between 400 units and 240 units, the analysis will be conducted based on ITT 1 population whereas the analyses will be based on ITT 2, 3 and 4 populations to assess the survival time by treatment cycle. Participants who are withdrawn from this study before Visit 2 are censored at the withdrawal date. All other participants who do not experience the event and is not withdrawn from study or of whom the date of Visit 2 is missing and is not withdrawn from study before the planned date of Visit 2 are censored at the Visit 2.

Survival function estimates will be summarized (survival probabilities and the number of participants at risk per time to event, and median in survival time) based on Kaplan Meier method. Kaplan Meier plots will be presented.

### **7.3.7. Time to Qualification for Retreatment**

These analyses will be based on ITT 1, 2 and 3 populations.

The number and percentage of event of interest will be presented by visit. Time to event data will be summarized using the descriptive statistics below and listed.

- The number of events and censored cases.
- Median survival time with the associated 95% CI.
- 25% and 75% survival time.

Survival analyses will be conducted using a Kaplan-Meier method. To graphically compare the survival functions between 400 units and 240 units, the analysis will be conducted based on ITT 1 population whereas the analyses will be based on ITT 2 and 3 populations to assess the survival time by treatment cycle. Participants who are withdrawn from this study before the events are censored at the withdrawal date. All other participants who do not experience the event and is not withdrawn from study are censored at the Last Observed Visit at the interim analyses or the final analyses.

Survival function estimates will be summarized (survival probabilities and the number of participants at risk per time to event, and median in survival time) based on Kaplan Meier method. Kaplan Meier plots will be presented.

Note that the retreatment is not allowed within 83 days from the previous treatment. Therefore, this event will not occur before 83 days later after the treatment/re-treatment.

CONFIDENTIAL

207660

